## 6. Project implementation plan

№ i/n	Name of task, activities for implementation of project tasks	Duration (in months)	Start and end date of work * (dd / mm / yy).	Years of project implementation, expected project results (in terms of tasks and activities)		
				2021	2021	2022
1.	Literature review on treatment of patients with failure of heart and lung within innovation technolog	6 months	01.01.2021-01.06.2021			
1.1	Literature review of patients on ECMO with using extracorporeal cytokine adsorber or hemoperfusion cartridge			Literature review for ECMO patients using an extracorporeal cytokine adsorber and an extracorporeal		

				hemoperfusion cartridge. Obtaining the results of the literary review.		
1.2	Literature review of septic patients with using extracorporeal cytokine adsorber or hemoperfusion cartridge			Literature review for septic patients using an extracorporeal cytokine adsorber and an extracorporeal hemoperfusion cartridge will be conducted. Obtaining the results of the literary review.		
2.	Recruiting patients on ECMO / septic patients with using extracorporeal cytokine adsorber or hemoperfusion cartridge depend of diagnosis	36 months	01.01.2021-31.12.2023	Initial patient condition will be studied	Initial patient condition will be studied	Initial patient condition will be studied
2.1	Examination of patients, verification of diagnosis and other procedure					
2.2	Study of directly clinical results of after using extracorporeal adsorbent on ECMO patients					
2.3	Study of directly clinical results of after using extracorporeal adsorbent on patients with sepsis.					
3.	Clinical and laboratory data will be analyzed on basis of clinical research	12 months	01.01.2023-31.12.2023			A protocol will be developed and optimized for the implementation of

						extracorporeal adsorber technologies for this category of patients
3.1	A protocol for optimization of introduction novel technology will be developed and implemented					
3.2.	Protocol implementation					
4.	Preparation of publications, reports, development of methodological guidelines	24 months	2022-2023		Article in international and local journals	Article in international and local journals
5.	Creation of intermediate and final reports	annually	2021-2023	Interim and final reports will be generated	Interim and final reports will be generated.	Interim and final reports will be generated.

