## 8. Expected results

The data of the Ministry of Health of the Republic of Kazakhstan show that annually in the country of terminal cardiac and pulmonary insufficiency is detected in 110-120 thousand people a year.

The clinical trial data will form the basis of practical protocols for extracorporeal membrane oxygenation (ECMO) and septic patients, the follow-up of which will improve organ repair, reduce postoperative complications, reduce mortality after surgery and improve quality of life.

The research results will be published in at least 3 (three) articles and (or) reviews in peer-reviewed scientific journals indexed in the Science Citation Index Expanded of the Web of Science database and (or) having a CiteScore percentile in the Scopus database of at least 35 (thirty five) , as well as in at least 1 (one) article or review in a peer-reviewed foreign or domestic edition recommended by the Committee for Monitoring in Education and Science of the Ministry of Education and Science of the Republic of Kazakhstan.

The results of a clinical study will improve the effectiveness of surgical treatment and reduce the level of complications and mortality, improve the quality of life of patients undergoing cardiac surgery. The introduction of a clinical protocol for the use of an extracorporeal adsorbent in this category of patients will allow standardizing this technique in the Republic of Kazakhstan.

The data obtained on the treatment of patients with heart and lung failure and organ restoration through the use of innovative technologies will provide the necessary information to improve the quality of tertiary care and the quality of life of patients in Kazakhstan and around the world. The developed methods can be used as new standards and recommendations both domestically and abroad through successful presentations at various conferences. If there are unique developments in the use of an extracorporeal adsorbent, patent applications will be filed.

In general, the expected effectiveness and efficiency of the proposed project will make a significant contribution to the development of transplantation, cardiac surgery and cardiology in Kazakhstan. In addition, the effective distribution of budgetary funds in accordance with the articles and amounts of expenditures will allow maximally concentrating the expenditure side of the implementation of this project to achieve the stated goals and objectives.

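### Data analysis, roll-out of a use protocol, articles and annual reports are scheduled inside open-label recruitment, with no bar on between-arm content and no room for the last day-30 follow-up

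*Combined protocol and SAP*

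**What the plan says.** Section 6 (Project implementation plan) dates the work as follows.

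- Row 2, recruitment: 36 months, "01.01.2021-31.12.2023". Items 2.2 and 2.3, on clinical results after adsorber use, sit under the same row.
- Row 3: "Clinical and laboratory data will be analyzed on basis of clinical research", dated "01.01.2023-31.12.2023". Item 3.1 reads "A protocol for optimization of introduction novel technology will be developed and implemented", and item 3.2 is its implementation. Neither item has its own dates, so I read both as falling in the row 3 window.
- Row 4, publications and guidelines: 24 months, 2022-2023, with the entry "Article in international and local journals".
- Row 5: "Creation of intermediate and final reports", annually over 2021-2023, with "Interim and final reports will be generated" entered for each year.

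Section 8 (Expected results) says "The research results will be published in at least 3 (three) articles", and the sentence goes on to let reviews count as well. It gives no date relative to the end of recruitment.

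Study Design describes an open-label randomised trial of 90 patients. Statistical studies lists tests to be run once data have been received. It gives no significance level, interim analysis, boundary, stopping rule or limit on access to accumulating results. Section 4 (Research methods and ethical issues) makes the cytokine measurements conditional on the investigators first seeing a clinical difference between groups, at no stated time. Outcome Measures lists cytokine response as the primary outcome for ECMO patients and as the first outcome for septic shock. Several outcomes run for 30 days, and ventilator-free days and survival are counted from randomisation.

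**The concern.** When analysis, publication and adoption of a treatment protocol overlap with randomisation in an unmasked trial, two things are at risk.

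The first is the error rate. If arms are compared more than once and significance at any look is claimed, the chance of a false positive exceeds the level of a single test.

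The second is bias. Only one recruiting centre is described, so the staff who see emerging results may also be choosing whom to enrol and treating later controls. Implementing an adsorber-use protocol while controls may still be allocated to no adsorber puts the control condition itself at risk. No statistical correction repairs that afterwards.

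There is also a completeness problem that needs no assumption about what the reports contain: the analysis window opens before recruitment ends and closes before the last possible patient has finished follow-up. A later reader could not tell how many looks came before a reported p-value, or on how many complete patients each rested.

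**Working it through.** The plan states no alpha, power or number of looks, so there is no figure of its own to reproduce.

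**Dates (from section 6 and the 30-day outcomes)**

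- Recruitment: 01.01.2021 to 31.12.2023 (36 months).
- Analysis and use protocol: 01.01.2023 to 31.12.2023 (12 months). This lies wholly inside recruitment, and both end on the same day.
- Articles: 2022-2023, all 24 months inside recruitment.
- Reports: those for 2021 and 2022 precede the end of recruitment; the 2023 report falls in its closing year.
- Last possible day 30: 31.12.2023 + 30 days = 30.01.2024, after the analysis window has closed.
- Latest enrolment that reaches day 30 by 31.12.2023: 31.12.2023 - 30 days = 01.12.2023. That leaves no time for analysis.

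The year-column headings of the table are unreliable in the text as read, so only the dates in the rows are used.

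**Patients still to enter when row 3 opens**

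Assuming uniform accrual and randomisation up to the last day of row 2: 90 x 24/36 = 60 enrolled by 01.01.2023, and 90 - 60 = 30 to come. This is an upper-end illustration. Row 2 also covers the study of results, so the last randomisation may be earlier, and results would not be known on the first day of a 12-month window.

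**Error rate if looks were comparative (illustration)**

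Assumptions, none of them in the plan: each look is a two-sided 5% test (|z| > 1.96), significance at any look is claimed, and corr(Zi, Zj) = sqrt(ti/tj) for information fractions ti < tj. The overall error is P(|Zi| > 1.96 at one or more looks) under no effect, obtained by simulation with 4 million draws.

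| Looks (information fraction) | Overall error |
|---|---|
| 1 only, or no comparative content earlier | 5.0% |
| 2/3 and 1 (correlation sqrt(2/3) = 0.816) | 7.7% |
| 1/3, 2/3 and 1 | 10.7% |

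The second line corresponds to one comparison at the opening of row 3, under uniform accrual. The third has no counterpart in the plan, which schedules no look at 1/3.

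**Does the text point to comparative content?**

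- Rows 3 to 3.2 develop and implement a use protocol, and section 8 says trial data will underpin such protocols. Pooled data cannot show whether an adsorber should be adopted, so this points to a comparison by arm.
- Section 4 requires a between-group clinical comparison before cytokines are measured, although cytokine response is the primary outcome. Its timing is not given.
- Against this, the row 2 result cells mention only the patients' initial condition, and Statistical studies places the analysis after data are received.

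**The case against.** The strongest reply is that this is a grant work plan, not an interim-analysis plan. The funding is split by year, and row 5 repeats the same entry, including a final report, every year, which reads as routine reporting to the funder. Section 8 lets reviews count as publications, and row 1 produces a literature review by mid-2021 that could feed the 2022 articles. Row 3 is the only data-analysis row, and it begins in 2023. Inflation also needs a claim or an action at an interim look. If nothing follows from the early looks, the final test keeps its nominal level.

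All of this stands. A reader might infer that the plan schedules yearly uncorrected efficacy tests and the release of arm-level results, with a false-positive rate of 10.7%. The documents do not support that. No passage says that a report compares arms, no comparison at one-third of the information is planned, and no error rate is stated that could be lost. Nor is it established that 30 patients would be randomised after results are known.

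The reply does not remove the overlap of rows 2 and 3, the placing of the use protocol inside recruitment, the missing day-30 cut-off, the untimed trigger in section 4, or the absence of any sentence keeping interim outputs free of between-arm data.

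**Conclusion.** The point holds as a defect of schedule and safeguard. Certain from the dates: analysis starts a year before recruitment is due to end, and it finishes 30 days before a patient enrolled on the last day completes follow-up. Also certain: nothing restricts reports or articles to pooled data in an open-label trial. That the reports or articles would contain between-arm results is permitted by the plan, not stated in it.

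The effect on type I error runs from none (5%, if interim content is non-comparative or nothing is claimed from it) to 7.7% per comparison for one extra look at two-thirds of the information. The 10.7% for three equally spaced looks only shows how the rate grows. These figures rest on an assumed two-sided 5% level and must not be cited as the plan's own. The possible bias from known results in unmasked staff cannot be sized from the documents.

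**What to change.** 1. In rows 3-5 and in Statistical studies, state that until the last patient completes day 30, reports and articles contain only recruitment figures, pooled baseline data, pooled safety data or literature-review material. The first between-arm efficacy analysis, and any use protocol based on it, come after that point.
2. If an arm-level interim look is required, name it in advance (timing, outcome, who sees it) and test it at p<0.001. One such look adds at most 0.001 to the error, so a final test at 5% gives at most 0.05 + 0.001 = 0.051.
3. Reconcile the end dates of rows 2 and 3 so that day-30 follow-up ends before the final analysis. Either last enrolment is about 01.12.2023 at the latest, and earlier to leave time for analysis, or the analysis end date moves later.
4. Remove the section 4 condition, so that cytokines are assayed in all patients as Outcome Measures requires.

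Cost: items 1, 2 and 4 are wording changes, but arm-level articles move to after recruitment. Item 3 is more than wording: either recruitment closes somewhat earlier, or the analysis runs into 2024, beyond the 2021-2023 project period in General information.

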## 8. Expected results

The data of the Ministry of Health of the Republic of Kazakhstan show that annually in the country of terminal cardiac and pulmonary insufficiency is detected in 110-120 thousand people a year.

The clinical trial data will form the basis of practical protocols for extracorporeal membrane oxygenation (ECMO) and septic patients, the follow-up of which will improve organ repair, reduce postoperative complications, reduce mortality after surgery and improve quality of life.

The research results will be published in at least 3 (three) articles and (or) reviews in peer-reviewed scientific journals indexed in the Science Citation Index Expanded of the Web of Science database and (or) having a CiteScore percentile in the Scopus database of at least 35 (thirty five) , as well as in at least 1 (one) article or review in a peer-reviewed foreign or domestic edition recommended by the Committee for Monitoring in Education and Science of the Ministry of Education and Science of the Republic of Kazakhstan.

The results of a clinical study will improve the effectiveness of surgical treatment and reduce the level of complications and mortality, improve the quality of life of patients undergoing cardiac surgery. The introduction of a clinical protocol for the use of an extracorporeal adsorbent in this category of patients will allow standardizing this technique in the Republic of Kazakhstan.

The data obtained on the treatment of patients with heart and lung failure and organ restoration through the use of innovative technologies will provide the necessary information to improve the quality of tertiary care and the quality of life of patients in Kazakhstan and around the world. The developed methods can be used as new standards and recommendations both domestically and abroad through successful presentations at various conferences. If there are unique developments in the use of an extracorporeal adsorbent, patent applications will be filed.

In general, the expected effectiveness and efficiency of the proposed project will make a significant contribution to the development of transplantation, cardiac surgery and cardiology in Kazakhstan. In addition, the effective distribution of budgetary funds in accordance with the articles and amounts of expenditures will allow maximally concentrating the expenditure side of the implementation of this project to achieve the stated goals and objectives.

